9.4.1.1. Danish National Health Registries

The analysis of the Danish population will be conducted with The Danish National Health registries, which includes data on reimbursed prescription drugs, medical encounter data, and related patient demographic and clinical variables. The National Prescription Registry (NPR), records medicine according to Anatomical Therapeutic Chemical (ATC) classification codes and product codes/names will be used to identify exposure to Mysimba. The NPR includes individual-level data on prescriptions filled by Danish residents at community pharmacies since 1995. The NPR contains 46 variables that describe each prescription, the patient receiving the prescription, the drug dispensed, the prescribing healthcare provider, and the pharmacy dispensing the drug. Additional data will come from the Danish National Patient Registry of hospital encounters, which includes information on diagnoses, selected treatments, and surgical procedures, and occurrence (not results) of diagnostic procedures of residents. The patient registry also includes administrative data consisting of the region the patient's residence, the admitting hospital, any referring healthcare providers or hospitals, reason for going to the hospital, and timing of hospitalization or treatment.

Data can also be linked to the Danish Laboratory Research Database, enabling researchers to further determine diagnoses and conditions through laboratory results. Denmark also has other registries that capture deaths, socioeconomic status, education, income, and social benefit data. Residents are identified and linked to all Danish registries by the Civil Personal Register (CPR) number and demographic information can be obtained from the Danish Civil Registration System. Based on current and projected Mysimba prescription sales and lack of reimbursement for Mysimba in Denmark, we do not anticipate that this database will include > 750 new users

of Mysimba who would be eligible for inclusion in the study as of December 31, 2023. Feasibility counts will be obtained at the time of the first interim report. Analysis of the database will be conducted at the time of interim analyses or final analysis if a total of >750 patients are eligible for study inclusion.

9.4.1.2. Finnish National Registries

The Finland Prescription Register includes data on prescription drugs that were reimbursed through the National Health Insurance Scheme since 2008. The data includes the medicines and corresponding products that have been purchased and reimbursed. The data are classified via the ATC system. Additionally, data will come from the Finnish Care Register for Health Care, which includes data on inpatient care as well as outpatient care. This includes data such as patient identification number, municipal residence, admission and discharge dates, diagnoses, any treatments provided, reason for seeking care, and medical procedures. Finland has other registries that capture social welfare services. All registries can be linked to the Population Register Centre, which contains demographic data on Finnish residents.

This data source was included at the request of the EMA.

Based on current and projected Mysimba prescription counts from the feasibility assessment, restriction of reimbursement of Mysimba to morbidly obese in Finland and assuming patients obtain approximately 6 Mysimba dispensings, 80% of patients are captured in databases and 80% of identified patients are new users with at least 365 days continuous eligibility in data source before first Mysimba prescription/dispensing, we anticipate having more than 750 new users of Mysimba who would be eligible for inclusion in the study as of December 31, 2023. Actual counts will be obtained at the time of the first interim report. Analysis of the database will be conducted at the time of interim analyses or final analysis if >750 patients are eligible for study inclusion, which is expected.

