- 6. Serotonin syndrome
- 7. Major adverse cardiovascular events (i.e., cardiovascular-related death, non-fatal myocardial infarction, or non-fatal stroke)

Deaths will also be described by treatment group, for those with vital status available.

- 7. Treatment discontinuation (assessed using ATC [outpatient, Nordic data] or NDC [US data])
- 8. Reason(s) for treatment discontinuation (obtained via ICD-10 codes in the 90 days prior to discontinuation)

All variables will be identified from the data sources via a pre-specified list of definitions (i.e., code lists; see Appendix 2). Occurrence of AESI based on diagnostic codes will be summarized for all patients, and for a subgroup of patients who do not adhere to conditions of the EU SmPC for the Scandinavian countries (adapted to local SmPC as needed) or to the FDA SmPC for the US. Such criteria include: not meeting appropriate criteria for the indication [obese (BMI \geq 30 kg/m²), or being overweight (BMI \geq 27 kg/m² to < 30 kg/m²) and having at least one weight-related co-morbidity (e.g., type 2 diabetes, controlled hypertension, or dyslipidemia) based on diagnostic codes. If BMI is not available, diagnostic and procedure codes for obesity and weight loss will be applied, recognizing that it will likely produce a more obese population than would be identified by BMI. Subgroup analyses will also be conducted to assess continuous treatment in patients with either renal or hepatic impairment.

Initiation of specific medications that could result with the occurrence of an event corresponding to an AESI (e.g., newly initiating anti-epileptic/seizure medication, newly initiating medications indicated for mania or depression) will also be tabulated. For hepatotoxicity, liver function tests can be used (when available) in addition to diagnostic codes.

For reason(s) patients who discontinue treatment (i.e., do not refill their prescription), events (potential AESIs and contraindications) and clinical status (magnitude of weight loss or gain)

Proprietary and Confidential:

occurring within the 90-day window prior to discontinuation will be summarized. It should be noted that weight may not be available in the Scandinavian registries.

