All citizens of these countries are represented in these national registries until death or emigration, providing virtually complete long-term follow-up. Identification of individuals by their unique personal identifier permits linkage to other national health databases (Laugersen et al., 2021). Thus, a large amount of specialized information from specific registries, such as hospitalization, prescription, heart disease, and death registries, can be linked for research (Schmidt 2015; Laugersen et al., 2021). The registries are highly complete and accurate due to the automation of their processes, as well as laws and other incentives motivating healthcare providers to collect and send the data electronically to their national databases (Gribsholt et al., 2019). The data from each country are expected to contain sufficient information to elucidate occurrence and determine levels of all variables, with the following exceptions which may be prone to misclassification due to limited coding in administrative and clinical data: obese or overweight with at least one comorbidity, neuropsychiatric conditions, history or current substance use or dependence, breastfeeding status, initial titration scheme and dose adjustments (expected to be unavailable since only one dose/pack type is available in the Nordic countries and no measure of titration scheme or adherence is included within the data), and reason(s) for medication discontinuation. Any country database with at least 750 patients with at least 365

days of data before the index Mysimba use and at least 548 days of availability in the data after the index date of Mysimba will be evaluated for whether there is sufficient required patient data to conduct this study. If there is sufficient data and uptake indicating that the database will reach more than 3,000 patients within the timespan of this drug utilisation and safety study, then it will be added to the data sources for evaluation. It should be noted that reimbursement varies in Scandinavia, with no reimbursement for Mysimba in Sweden and Denmark, and reimbursement in Norway and Finland restricted to morbidly obese patients who are at higher risk of cardiovascular and other events.

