9.4.2. United States Data Source

An EHR or claims-based integrated database across multiple healthcare systems in the United States, providing a representative mix of US Commercial Insurance and Medicare (major systems of health insurance in the US) has been selected. Arcadia Data Research was chosen as the US data for this study because of their approximately ten-year history of successfully curating data for health systems that are substantially involved in value-based care, which necessitates high-quality clinical data across the included patient populations. Data incorporated into the US dataset will include electronic medical records from multiple systems, laboratory test orders, and prescription data. Moreover, a sizeable proportion of the EHR population will also have their health insurance claims records linked in their final (adjudicated) form. The typical data extract will include (but is not limited to): patient demographics and characteristics (including height and weight or BMI if available), medical encounters, appointments, provider data, charges, assessments, immunizations, health maintenance and medical history, laboratory orders/results, vital signs (e.g., blood pressure, heart rate), patient insurance, prescriptions and active medications, problem lists, and patient allergy information. EHR data are sourced from large integrated delivery networks, academic medical centres, ambulatory care, primary care, core hospitals, and others. The data are coded in standard vocabularies used within the US, including ICD-10, NDC, CPT, LOINC, etc. Additional information, such as social determinants of health will be captured, if available. The data are expected to contain sufficient information to elucidate occurrence and determine levels of all variables, with the following exceptions which may be prone to misclassification due to limited coding in administrative and clinical data: neuropsychiatric conditions, history or current substance use or dependence, breastfeeding status, and reason(s) for medication discontinuation.

The integration of claims data for a subset of patients will be important for this study in order to capture pharmacy prescriptions dispensed and for better capture of MACE events. The selected database will be described in more detail in the US SAP.

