9.7. Data Analysis

9.7.1. Timing of Feasibility, Interim, and Final Analyses

Prior to study start, feasibility was conducted annually.

One cohort per country will be extracted each time the database is opened. Per database, the following analyses will be conducted:

- 1. ongoing data review, for each of the participating Nordic countries
- 2. a first (interim) analysis when a database size reaches 750 patients with up to 548 days of activity in database after index date
- 3. a second (interim) analysis when an additional 2,250 patients (total 3,000 patients) with a Mysimba/Contrave index date are included in a database with up to 548 days of calendar time available in the database after the index date
- 4. a final analysis of the database will be conducted for the final report including all patients from the EU data sources meeting the inclusion criteria for the study as of 15 February 2025. If >3000 patients are available at the time of an interim analysis, the final report for

that database will be submitted one year after data is accessible. If final data is available 31 Dec 2024, the final report will be submitted by 31 Dec 2025.

All analyses will be performed separately in each country. All patients in the study will be included in the analysis, regardless of whether there is evidence of any contact with the health system (as registered by any data in the database) after inclusion into the study. One interim and one final analysis will be conducted per country. A final report will be generated when the last database in the study conducts the final analysis (when the last database has >3000 Mysimba patients, or 31 Dec 2025, whichever comes first). The final analysis from the four participating Nordic countries will be included in that report which will be accompanied by synthesis of findings, discussion, and interpretation across all Nordic databases.

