Name of the main author of the protocol.				
Name of the main author of the protocol:				
Date: dd/Month/year				
Signature:				

15. Appendix 2. Code lists

Mysimba ATC: A08AA62 Contrave NDC: search terms – Contrave, naltrexone, bupropion Naltrexone ATC: N07BB04, A06AH01, N02AA56	
Contrave NDC: search terms – Contrave, naltrexone, bupropion	
Naltrexone ATC: N07BB04, A06AH01, N02AA56	
NDC: search terms – naltrexone	
Bupropion ATC: N06AX12	
NDC: search terms – bupropion	
Concomitant Medications	
CYP2B6 inhibitors See Appendix 2A	
CYP2B6 inducers See Appendix 2A	
CYP2B6 substrates See Appendix 2A	
CYP2D6 substrates See Appendix 2A	
Drugs that lower Propoxyphene, remifentanil, sufentanil, tapentadol, tramadol,	
seizure threshold baclofen, buspirone, dalfampridine, lithium, mefenamic acid,	
amphetamine, benzphetamine hydrocholoride, dextroamphetan	mine,
hydroxyamphetamine hydrobromide, lisdexamfetamine dimes	
methamphetamine hydrochloride, cocaine, phenylpropanolam	
dexamphetamine, methylphenidate	
Opioid or opiate ATC: N02A;	
agonist	
Opium alkaloids & ATC: R05DA, N02AA	
derivatives	
MAOI ATC: N04BD, N06AF, N06AG	
Seizures ICD-10: G40	
Increase in blood ICD-10: R00.0, R03.0	
pressure or heart rate	
Hypersensitivity, ICD-10: T78, L51	
including Stevens-	
Johnson	
Serotonin syndrome ICD-10: T43.225A	
Suicidality ICD-10: R45.851, T14.91	
Diabetes ICD-10: E10-E11	
Dyslipidaemia ICD-10: E78	
Neuropsychiatric	
conditions:	
Mania ICD-10: F30	
Bipolar disorder ICD-10: F31	

N4 : 1 :	ICD 10 F22
Major depressive	ICD-10: F33
disorder	ICD 10 F50 0
Anorexia nervosa	ICD-10: F50.0
Bulimia	ICD-10: F50.2
Hypertension	ICD-10: I10-I16
TT . 11 1	
Uncontrolled	ICD-10: I10-I16 (with Systolic ≥140 mmHg or diastolic ≥90 mmHg)
hypertension	10D 10 N10 0 N10 5
Moderate or severe	ICD-10: N18.3-N18.5
renal impairment	
End stage renal	ICD-10: N18.6
disease	
Hepatic impairment	ICD-10: K70, K72-K75
Central nervous	ICD-10: C72
system tumour	
Substance	ICD-10: F10-F19
abuse/dependency	
	ATC: N06AA11
Protriptyline*	NDC: search terms – protriptyline
Dannanidal (Anarril)*	ATC: N05AD07
Benperidol (Anquil)*	No NDC
Flupentixol	ATC N05AF01
(Depixol)*	No NDC
Fluphenazine	ATC: N05AF02
(Modecate,	NDC: search terms – fluphenazine
Prolixin)*	•
Levomepromazine	ATC: N05AA02
(Nozinan)*	No NDC
Loxapine	ATC: N05AH01
(Loxitane)*	NDC: search terms – loxapine
	ATC: N05AE02
Molindone (Moban)*	NDC: search terms – molindone
	ATC: N05AC01
Periciazine*	No NDC
Sulpiride (Dolmatil,	ATC: N05AL01
Sulpor)*	No NDC

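### Finland's register as described holds only reimbursed, morbidly obese users, and no Nordic source is shown to hold the BMI or blood-pressure values that two compliance criteria need

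*Protocol*

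**What the plan says.** **Finnish exposure.** Section 9.4.1.2 says "The Finland Prescription Register includes data on prescription drugs that were reimbursed through the National Health Insurance Scheme since 2008" and then "The data includes the medicines and corresponding products that have been purchased and reimbursed". Section 9.4.1 describes "reimbursement in Norway and Finland restricted to morbidly obese patients who are at higher risk of cardiovascular and other events"; section 9.1 lists the same restriction. Section 9.4.1.2 uses the restriction to project patient numbers but does not carry it through to compliance. Appendix 3 rates Finnish dispensing data Yes.

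**Indication.** Primary objective 2 (section 8) asks for the number and percentage of patients compliant with the SmPC, including the obesity or overweight-plus-comorbidity criterion. Section 9.3.2 adds: "If BMI is not available, diagnostic and procedure codes for obesity and weight loss will be applied". Appendix 3 gives BMI, height, weight and reason for treatment an entry (Partial) for the US only. Appendix 2, named in section 9.3.2 as the source of all definitions, has no row for obesity, overweight or weight-loss counselling.

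**Uncontrolled hypertension.** Appendix 2 defines it as "ICD-10: I10-I16 (with Systolic ≥140 mmHg or diastolic ≥90 mmHg". Section 9.4.2 lists "vital signs (e.g., blood pressure, heart rate" among the US data. None of the four Nordic descriptions mentions blood pressure. Section 9.3.3 hedges the variable with an if-possible, while Appendix 3 rates it Yes for all five countries.

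**Use of the results.** Compliance is a primary objective and defines the subgroups for the AESI comparison (sections 8 and 9.7.3.1). The final report adds a "synthesis of findings, discussion, and interpretation across all Nordic databases" (section 9.7.1).

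**The concern.** In Finland the data source selects on the characteristic being measured. If only reimbursed purchases are recorded and only the morbidly obese are reimbursed, use below the labelled BMI cannot be seen, however common it is. In the other Nordic registers such users can enter the cohort, but nothing measured separates an on-label patient who was never coded from a patient who is not obese. For uncontrolled hypertension, a contraindication is promised for countries where its defining measurement is not described.

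At stake are the BMI component of the primary compliance percentage, one contraindication component, the compliant versus non-compliant AESI comparison built on them, and any reading of differences between countries. The study is meant to inform whether the SmPC should be revised (section 7).

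**Working it through.** The plan gives no compliance figure to reproduce. The check sets sections side by side and adds bounding arithmetic.

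**1. Is the selection specific to Finland?** Section 9.4.1.3 describes the Norwegian database as holding all dispensed prescription drugs, and section 9.4.1.4 says the same of Sweden. Section 9.4.1.1 opens by mentioning reimbursed drugs for Denmark, but then describes prescriptions filled at community pharmacies; Mysimba is not reimbursed there. Only the Finnish text, stated twice, limits the register to reimbursed purchases. The selection is Finnish, not Nordic.

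**2. How far could Finnish compliance be from that of all users?** Let k be the share of users captured and u the BMI compliance of those not captured. Assume every captured user truly meets the BMI criterion, as the reimbursement rule implies. Then compliance among all users = k + (1 − k) × u.
- k = 0.80, the feasibility assumption in section 9.4.1.2: 0.80 + 0.20 × u, so 80% (u = 0) to 100% (u = 1).
- k = 0.50 (my assumption): 50% to 100%.

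The 80% is not tied to the reimbursed share of sales, so it is only a guide to k.

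**3. What if a missing code were read as not meeting the indication?** Let C be true compliance and Se the sensitivity of the codes, with no false-positive codes. Apparent non-compliance = 1 − Se × C. The documents give neither input, so both are assumed.

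| Se | C = 1.00 | C = 0.95 | C = 0.90 |
|---|---|---|---|
| 0.2 | 80% | 81% | 82% |
| 0.4 | 60% | 62% | 64% |
| 0.6 | 40% | 43% | 46% |
| 0.8 | 20% | 24% | 28% |
| 0.9 | 10% | 14.5% | 19% |

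The formula applies to Finland as elsewhere, because Finland also lacks BMI. With C = 1 there, the reported figure would still be 10% to 80%.

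On this component, the share of the apparent non-compliers who are truly on-label is C(1 − Se) / (1 − Se × C). With C = 0.95 it is 0.38 / 0.43 = 88% at Se = 0.6, and 0.095 / 0.145 = 66% at Se = 0.9. The AESI contrast on this criterion would then largely compare on-label users with each other.

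**4. Is incomplete coding plausible?** Danish diagnoses come from hospital encounters (section 9.4.1.1), and Swedish ones from inpatient and hospital-based outpatient care (section 9.4.1.4). No primary-care diagnosis source is described for either. Section 9.9.1 nevertheless says BMI and weight are likely to be present and rarely missing, which Appendix 3 does not support for any Nordic source.

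**5. Hypertension.** The definition needs a reading, and readings are described only for the US. Appendix 3 does have rows for laboratory and diagnostic testing results (Yes for Sweden, Limited for the other Nordic countries), but neither row names blood pressure. A Nordic Yes is therefore unsupported.

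**The case against.** The strongest reply is that the handling of absent BMI belongs to the SAP. Section 9.3.2 sends details there and mentions prediction of BMI. Section 9.7.2 allows adaptation when BMI is not accessible, and section 9.7.3.1 again defers to the SAP. Section 9.7.5 describes patients with missing BMI separately, and bars imputed values from the indication classification. Nowhere is a missing code declared to mean non-compliance. This stands: step 3 of the working shows what follows if that reading is adopted, not what the plan prescribes. But the protocol does not rule the reading out and creates no class for patients whose indication cannot be judged.

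Much is also disclosed. The reimbursement restriction is stated repeatedly. Section 9.4.1 names the obesity or overweight criterion as prone to misclassification. Section 9.9.1 mentions treatment outside the reimbursed system, though generically and as a matter of exposure measurement. Analyses are run separately by country, the synthesis is narrative, and section 9.7.2 reports each component, so the BMI criterion stays visible. Denmark may never reach 750 patients (section 9.4.1.1). Appendix 3 is a draft, to be confirmed in the SAP. All this limits the damage; none of it tells the reader that the Finnish figure describes reimbursed users only, or reconciles the hypertension entry with its definition.

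A reader might go further and infer that Finland will report no BMI non-compliance while Denmark and Sweden report very high values. The documents do not support that contrast: Finland would be judged by codes too, so uncoded Finnish patients could fail as well. Nor do they support the inference that Nordic compliance as a whole reflects data capture and not prescribing. Age and many contraindications are rated available in the Nordic sources.

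**Conclusion.** The point holds in limited form. Two parts rest on the protocol's text alone:
- Finnish off-label use by BMI is largely unobservable as the register is described.
- Uncontrolled hypertension is rated available in four countries for which no blood-pressure source is described.

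A third part is conditional: without BMI, the Nordic indication figure cannot be separated from coding completeness unless patients without a code have a class of their own.

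On size, at the protocol's 80% capture, BMI compliance among all Finnish users could lie up to 20 percentage points below that of captured users, assuming captured users all meet the reimbursement rule. Reading a missing code as non-compliance would push apparent compliance the other way, by 10 to 80 points for assumed sensitivities of 0.9 to 0.2 when true compliance is 100%. The two effects oppose each other, so the figure would be hard to interpret rather than biased in a known direction. The change should be made before compliance results are reported.

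**What to change.** - Label all Finnish results as reimbursed users. State that BMI-criterion compliance there does not describe all Finnish users, and keep it out of cross-country comparison on that criterion. Finland, included at the EMA's request, stays in the study.
- Where neither BMI nor a relevant code exists, class the patient as indication not ascertainable. Report non-compliance with two bounds: these patients all compliant, and all non-compliant.
- Add the obesity, overweight and weight-loss codes to Appendix 2, and bring section 9.9.1 into line with Appendix 3 on BMI and weight.
- In Appendix 3, change uncontrolled hypertension to not available wherever blood pressure is absent, and leave it out of those countries' contraindication composite. If a Nordic source does hold readings, name it.

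The cost is protocol and SAP wording plus a few table rows. The downside is that Nordic indication compliance becomes a range over fewer criteria. The range may be wide, because codes can confirm obesity but rarely show its absence: the lower bound for non-compliance would be near zero and the upper bound close to the values in the table.
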